5.5.1.2 Other Antihypertensive Medications and Medications for Heart Failure

The use of beta-adrenergic blockers (bisoprolol, sustained release metoprolol and carvedilol are the preferred beta-adrenergic blockers but are not required) and diuretics are permitted if the subject has been on a stable dose at least 28 days prior to Screening. However, recommendations regarding the timing of any medication as described in Section 5.5 should be followed to minimize the possibility of a drug interaction. For all medications, clinical response should be monitored as higher doses may be required during concomitant treatment with patiromer (see Section 5.5).

In order to control BP at any time during the study, non-RAAS inhibitor, non-potassium sparing diuretics and antihypertensive drugs that do not affect potassium levels (e.g., calcium channel blocker, alpha blocker and alpha-2 agonist) may be added or modified per the Investigator's discretion.

While every effort should be made to keep the above medications stable during the entire study, doses may be adjusted at the discretion of the Investigator. Subjects being treated with a diuretic and who are not on a consecutive daily dosing regimen and who are scheduled to take a dose of the diuretic on the day of the study visit must be instructed to take their diuretic dose after the local and

central laboratory blood has been drawn for potassium evaluation. Additional medications that are permitted to treat the symptoms or complications of heart failure are aspirin, hydralazine, and nitrates. Doses of these medications do not need to have been stable prior to screening and can be adjusted during the study.

5.5.2 Permitted Medications for Anti-Rejection of Transplant

Subjects treated with tacrolimus, mycophenolate mofetil or cyclosporine should be on a stable dose for at least 14 days prior to Screening and expected to remain on the stable dose during the PD / Dose Finding Phase (first 14 days) of the study. In the event that the dose of the anti-rejection medication requires adjustment during the 14-Day PD / Dose Finding Phase, the study Medical Monitor should be contacted to determine if discontinuation of patiromer and potential early termination from the study is required. Small changes in dose during the 14-Day PD / Dose Finding Phase may be acceptable. During the Long-term Treatment Phase, dose adjustments of tacrolimus, mycophenolate mofetil or cyclosporine are allowed at the discretion of the Investigator.

Recommendations regarding the timing of any medication as described in Section 5.5 should be followed to minimize the possibility of a drug interaction. Clinical response and/or blood levels where possible should be monitored as higher doses may be required during concomitant treatment with patiromer.

5.5.3 Permitted Prophylactic Trimethoprim Antibiotic

Trimethoprim (including cotrimoxazole) used for prophylaxis of infections (e.g., *Pneumocystis carinii* pneumonia, urinary tract infection) is permitted provided the dose has been stable for 14 days prior to Screening and is expected to remain stable during the 14-Day PD / Dose Finding Phase.

5.5.4 Permitted Fludrocortisone

Fludrocortisone use is permitted provided that the subject has been on a stable dose at least 28 days prior to screening and the dose is expected to remain stable during the 14-day PD / Dose Finding Phase. In the event that prescription for fludrocortisone requires adjustment during the 14 Day PD / Dose Finding Phase, the study Medical Monitor should be contacted. During the Long-Term Treatment phase, investigators should avoid making changes in fludrocortisone dose; however, changes in this medication are acceptable for safety reasons (e.g., hypokalemia, increase blood pressure, edema). For subjects taking fludrocortisone who experience hypokalemia, the investigator should adjust fludrocortisone dose prior to making changes in the patiromer dose if possible, giving due consideration to patient safety and the degree of hypokalemia.

5.6 Prohibited Medications

During the 14-day PD / Dose Finding Phase, the following medications will be prohibited:

- sodium or calcium polystyrene sulfonate
- sodium zirconium cyclosilicate
- drospirenone

During the Long-Term Treatment Phase, the following medications will be prohibited:

- sodium or calcium polystyrene sulfonate
- sodium zirconium cyclosilicate
- drospirenone

6 TRIAL PROCEDURES

Refer to the Schedule of Events (see Appendix A and Appendix B) for the frequency and timing of the required study assessments.

Laboratory-related eligibility criteria will be based on values obtained locally, specifically potassium, creatinine, ALT/AST, CBC, and pregnancy test (females of child-bearing potential). The central laboratory results will be used for the establishment of baseline values, safety, and for all statistical analyses.

The Investigator should base decisions related to potassium (e.g., patiromer titration) on the values obtained locally at the study site only. Central laboratory potassium results will be used for the efficacy analyses and, for the purpose of the Investigator, as supplemental safety information. Central laboratory potassium results should not override any decisions made by the Investigator based on local potassium measurements.

The Investigator must review all laboratory and any ECG results as soon as possible after the results are available. Of particular importance are the timely identification of any out-of-range potassium laboratory results. If the Investigator is concerned regarding any potassium value, a re-test of potassium level and/or ECG evaluation for electrophysiological consequences can be initiated by the Investigator at his/her discretion.

To avoid hemolysis of samples, specimen collection and handling must strictly follow specific instructions provided in the Laboratory Manual. Blood samples for potassium assessment (local and central laboratory) should be collected at approximately the same time (preferably in the morning) for the same subject at all Study Visits (Sections 6.1 and 6.2).

6.1 Screening Visit(s)

Before any study-specific procedures are performed, the legally authorized representative and subject must receive an explanation of all study procedures that is described using age appropriate language. The legally authorized representative must sign and date a written informed consent form (ICF) and the subject must sign and date the assent (when applicable) approved by an institutional review board (IRB) or Ethics Committee (EC) (see Section 12.1 for additional requirements). The timing of the Screening Visit (and all subsequent visits) should take into account planned absences at the research facility and the need for study visits according to the Schedule of Events (see Appendix A and Appendix B).

The subject will be assigned a unique study subject identification number, which will be generated during Screening Visit registration in IWRS.

Subject's eligibility will be assessed during a Screening Period with up to two visits (Screening Visit 1, Screening Visit 2). Eligibility for this study requires the presence of hyperkalemia assessed by two blood or serum potassium measurements performed on separate days; qualifying potassium values are 5.1 to < 6.5 mEq/L. A standard of care local potassium value measured within 42 days to 2 days prior to Screening may be used for one of the potassium values to assess eligibility. The following scenarios are allowed for obtaining the two qualifying potassium values (5.1 to < 6.5 mEq/L):

- For subjects **with a recent standard of care potassium measurement**, the two qualifying potassium values will be the most recent standard of care potassium measurement obtained from 42 days to 2 days prior to Screening Visit 1 and the local potassium measurement at Screening Visit 1
- For subjects **without a recent standard of care potassium** measurement within 42 days to 2 days prior to Screening Visit 1, the first qualifying potassium value will be obtained at Screening Visit 1 and the second at Screening Visit 2, occurring 2 to 7 days after Screening Visit 1

Subjects who screen fail may be rescreened once upon approval of the Medical Monitor, see Section 6.1.3 for details.

For subjects who meet all eligibility criteria at either Screening Visit 1 or Screening Visit 2, that visit should be converted to the Day 1 Visit (Baseline). In cases where this is not possible, eligible subjects must return the next day to complete the Day 1 Visit.

6.1.1 *Subjects with Standard of Care Potassium Measurement*

Subjects are requested to arrive in the morning of **Screening Visit 1**. The blood specimen obtained will be used to measure potassium locally (a serum sample from the specimen will be sent to the central laboratory for subjects with confirmed eligibility). The following screening activities will be performed at **Screening Visit 1**:

- Legally authorized representative informed consent and subjects' assent (when applicable) signing
- Subject's registration in IWRS
- Review of inclusion and exclusion criteria
- Demographics
- Review of medical history
- Physical examination
- Body weight and height
- Vital Signs (resting heart rate and sitting BP)
- 12-Lead ECG
- Blood or serum potassium levels measured locally

- Blood or serum chemistry tests including AST, ALT, magnesium, creatinine and eGFR measured locally
- Local hematology (CBC including WBC, RBC, hemoglobin, hematocrit, and platelet count)
- Local urine pregnancy test (female subjects of child-bearing potential only). A serum pregnancy test will be performed in the event of a positive or equivocal urine pregnancy test result
- AE assessment
- Concomitant medication assessment

The Investigator shall review all screening information as soon as possible for safety and eligibility. Subjects who meet all eligibility criteria should have their **Screening Visit 1** converted to the Day 1 (Baseline Visit) where the starting dose of patiomer is administered to the subjects if scheduling allows. In cases where this is not possible, eligible subjects must return the next day to complete the Day 1 Visit.

6.1.2 *Subjects without Standard of Care Potassium Measurement*

6.1.2.1 Screening Visit 1

The following screening activities will be performed at **Screening Visit 1**:

- Legally authorized representative informed consent and subjects' assent (when applicable) signing
- Subject's registration in IWRS
- Blood or serum potassium levels (measured locally)
- Demographics
- Medical history (can be performed at Screening Visit 1 or Screening Visit 2)
- Physical Examination (can be performed at Screening Visit 1 or Screening Visit 2)
- Height (can be measured at Screening Visit 1 or Screening Visit 2)
- Vital Signs (resting heart rate and sitting BP)
- 12-Lead ECG (can be measured at Screening Visit 1 or Screening Visit 2)
- AE assessment
- Concomitant medication assessment

6.1.2.2 Screening Visit 2

Subjects with confirmed eligibility for hyperkalemia (a local potassium level of 5.1 to < 6.5 mEq/L) from Screening Visit 1 will be requested to return 2 to 7 days after Screening Visit 1 for Screening Visit 2. Subjects should arrive in the morning of **Screening Visit 2**. The blood specimen obtained will be used to measure potassium locally (a serum sample from the specimen will be sent to the central laboratory for subjects with confirmed eligibility).

The following screening activities will be performed at **Screening Visit 2**:

- Subject's registration in IWRS
- Review of inclusion and exclusion criteria
- Body weight
- Vital Signs (resting heart rate and sitting BP)
- Blood or serum potassium levels measured locally
- Blood or serum chemistry tests including AST, ALT, magnesium, creatinine and eGFR measured locally
- Local hematology (CBC including WBC, RBC, hemoglobin, hematocrit, and platelet count)
- Local urine pregnancy test (female subjects of child-bearing potential only). A serum pregnancy test will be performed in the event of a positive or equivocal urine pregnancy test result or if the subject is anuric
- AE assessment
- Concomitant Medication Assessment

The Investigator shall review all screening information as soon as possible for safety and eligibility. Subjects who meet all eligibility criteria should have their Screening Visit 2 converted to the Day 1 (Baseline Visit) where the starting dose of patiomer is administered to the subjects if scheduling allows. In cases where this is not possible, eligible subjects must return the next day to complete the Day 1 Visit.

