4.1 Inclusion Criteria

Subjects must meet ALL the following criteria:

1. Written assent (when applicable) and written informed consent by a legally authorized representative provided prior to participation in the study
2. Age 2 – < 18 years old (subject's age should not exceed that of the age cohort into which s/he is enrolled for at least the entire 14 days of the PD / Dose Finding Phase)
3. Pediatric subjects with CKD and eGFR < 90 mL/min/1.73 m² calculated using the Schwartz formula as described in Section 7.2, including renal transplant subjects, based on local creatinine measurement at Screening
4. Two blood or serum potassium measurements of 5.1 to < 6.5 mEq/L performed on separate days (see Section 6.1)
5. In the opinion of the Investigator, the subject is expected to require treatment for hyperkalemia for at least 6 months
6. If taking any RAASi, beta blockers, fludrocortisone or diuretic medications, must be on a stable dose for at least 28 days prior to Screening
7. Females of child-bearing potential must be non-lactating, must have a negative pregnancy test at Screening, and must have used an effective form of contraception (e.g., abstinence, hormonal, chemical, physical barrier, etc.) for at least 1 month before patiromer administration. Subjects of child-bearing potential must agree to continue using contraception throughout the study and for 1 month after the last dose of patiromer

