5 STUDY TREATMENTS

5.1 Treatment Blinding

The study is open-label and non-randomized.

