5 ENDPOINTS AND VISIT WINDOWS

5.1 Efficacy Endpoints

5.1.1 *Primary Efficacy Endpoint*

Changes from baseline to Day 14 in serum potassium levels will be summarized by starting dose and age group using descriptive statistics. Baseline potassium will be the last non-missing central laboratory serum potassium value prior to first dose of patiromer. Descriptive statistics include mean, standard deviation, and 95% confidence intervals.

5.1.2 *Secondary Efficacy Endpoints*

- Proportion of subjects with serum K⁺ levels in the range of 3.8 – 5.0 mEq/L at Day 14 (Initial PD / Dose Finding Phase)
- Proportion of subjects with serum K⁺ levels in the range of 3.8 – 5.0 mEq/L by visit at any time through Month 6 (Long-Term Treatment Phase)

Proportions and associated exact 95% confidence interval will be presented.

5.1.3 *Subgroups*

The primary and secondary efficacy analyses may be performed for the following subgroups:

- Sex (male versus female)
- Age (12 – <18 versus 6 – <12 versus 2 – <6 years)
- Race (white versus non-white)

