7.3 Demographics and Baseline Characteristics

Demographics and baseline characteristics will be summarized for the ITT and safety population.

The summary of demographic information will include age, gender, race and ethnicity. The summary of patient characteristics at baseline will include, weight, height, and BMI. Baseline medical history will include chronic kidney disease and its etiology, whether patient was on peritoneal dialysis, whether patient ever received a renal transplant, whether patient had diabetes mellitus and its type, , heart failure and its type, ejection fraction percentage, baseline serum potassium and eGFR.

Listings of demographics and baseline characteristics will also be provided.

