7.9.2 Secondary Efficacy Analysis

Number and proportion of subjects with central serum potassium levels in the range of 3.8 – 5.0 mEq/L at Day 14 (Initial Pharmacodynamic / Dose Finding Phase) and proportion of subjects with central serum potassium levels in the range of 3.8 – 5.0 mEq/L by visit through Month 6 (Long-Term Treatment Phase) will be presented.

Proportions will be provided along with the 95% confidence intervals, obtained using Exact (Clopper-Pearson) method.

Central serum potassium and mean changes in serum potassium at each scheduled visit will be presented graphically. Central and local laboratory potassium values from serum samples will be included in listings.

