7.10.3 Clinical Laboratory Tests

For central laboratory test summaries by visit, the central laboratory measurements at scheduled visits will be used if available. The visit name from the central laboratory will be used to determine whether a visit is scheduled or unscheduled.

If a laboratory result from a visit is retested and the central laboratory subsequently determines the original result to be valid, the original result for that visit will be used in analysis, and the second (i.e. ‘retested’) value will be ignored. Otherwise, if the central laboratory detects an error through the retesting, the retested value will be used in analysis as the measurement for that visit.

The baseline central laboratory value is defined as the last non-missing central laboratory value collected on or before the date of the first dose of study medication.

All serum chemistry, hematology, serum fluoride, and plasma parathyroid hormone level results and change from baseline will be summarized with descriptive statistics at each scheduled visit.

The incidence of laboratory test results in ranges of interest will be summarized. These summaries will include but are not limited to the following:

- Serum potassium < 3.0, < 3.5, < 3.8, > 5.0, and \geq 5.5 mEq/L
- Serum magnesium < 1.4, < 1.2, and < 1.0 mg/dL
- Serum calcium > 10.2 mg/dL

Laboratory shift tables from baseline to end of dose finding period and baseline to end of treatment will be presented for serum calcium, magnesium and phosphate.

Listings will be provided for all laboratory parameters. Listings will include test results at both scheduled and unscheduled visits.

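### Does taking the central baseline potassium from the qualifying specimen, with no control arm, call for a potassium shift table or another added analysis?

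*Protocol*

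**What the plan says.** Entry requires two local potassium values of 5.1 to below 6.5 mEq/L on separate days (Protocol 4.1, criterion 4). On both screening routes (Protocol 6.1.1 and 6.1.2.2) the blood drawn for the second value is split: the local result decides eligibility and "a serum sample from the specimen will be sent to the central laboratory for subjects with confirmed eligibility". Protocol 6.1 makes that visit Day 1 by default; returning the next day is the fallback. SAP 5.1.1 then states: "Baseline potassium will be the last non-missing central laboratory serum potassium value prior to first dose of patiromer".

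There is no comparator: "The study is open-label and non-randomized" (Protocol 5.1). The primary endpoint is the mean central change to Day 14 with a 95% interval. The in-range proportion (3.8 to 5.0 mEq/L) is secondary, with an exact interval (SAP 7.9.2).

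SAP 7.10.3 plans shift tables, but only for other analytes: those from baseline to "end of dose finding period and baseline to end of treatment will be presented for serum calcium, magnesium and phosphate". For potassium the SAP plans a baseline summary ("ejection fraction percentage, baseline serum potassium and eGFR" are among the characteristics in 7.3, with quartiles, minimum and maximum under 7.1), results and change by visit, incidence by threshold, and graphs. SAP 7.9.2 adds: "Central and local laboratory potassium values from serum samples will be included in listings".

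**The concern.** Selecting children on a high value and then using the same specimen as baseline builds that day's upward deviation into the baseline. When the deviation fades, potassium falls without any drug, and with no control arm the fall is read as drug effect. Neither document mentions regression to the mean.

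A second worry is mixed in with the first. Eligibility is local and analysis is central, so a child can qualify at 5.1 locally, have a central baseline of 5.0 or lower, and still count as in range at Day 14. The planned tables give baseline and Day 14 separately, so they do not show how many such children there are. If the effect were large, the primary change and the in-range rate would both overstate patiromer's activity. The omission of potassium from the shift tables then looks odd, since it is the primary variable.

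**Working it through.** **The plan's own figure.** Protocol 9.3 and SAP 2.3 give a lower exact 95% bound of 73% for 12 of 12 in range. Check: 0.025^(1/12) = 0.735. It reproduces and does not depend on baseline.

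**Where each effect comes from.** Let T be a child's usual potassium, b the day's deviation and e the assay error.

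- Second local value: T + b2 + e(local)
- Central baseline, same specimen: T + b2 + e(central)
- Day 14 with no drug: T + b14 + e(14)

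The expected no-drug change among enrolled children is E(b14) - E(b2 | qualified) = 0 - E(b2 | qualified), which is negative. With a baseline from another, independent day it is 0. Being in range at Day 14 means 3.8 <= T + b14 + e(14) <= 5.0. That expression has no baseline term, so the no-drug in-range rate comes from the entry threshold alone. A central baseline of 5.0 or lower after a qualifying local value is disagreement between laboratories on one specimen, a third and separate matter.

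**Size.** The documents give no paediatric mean or within-child SD, so these inputs are assumed: between-child SD 0.4; usual mean 4.8, 5.0, 5.2 or 5.4; within-child SD 0.2, 0.3 or 0.4; assay SD 0.1 or 0.2 mEq/L; values rounded to 0.1; both local values 5.1 to below 6.5; no drug effect. That is 24 settings, simulated with 3 million children each before selection. The middle settings (within-child SD 0.3, assay SD 0.1) give:

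| Usual mean | Change to Day 14 | In range at Day 14 | In range at central baseline |
|---|---|---|---|
| 5.0 | -0.104 | 22.2% | 6.8% |
| 5.2 | -0.074 | 16.4% | 5.1% |
| 5.4 | -0.046 | 11.4% | 3.6% |

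All 24 settings span -0.02 to -0.22 mEq/L, 7% to 37% and 3% to 18%. A second grid (mean 4.6 to 5.2, between-child SD 0.4 or 0.5, assay SD 0.1) spans -0.03 to -0.27, 10% to 43% and 4% to 12%.

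**Check on the mechanism,** at usual mean 5.0 in the middle setting: mean baseline 5.474, Day 14 5.370, difference -0.104. A separate-day baseline gives 0.00, and the 22.2% in range is unchanged. If only one qualifying value were required, the change would be -0.150, so the two-value rule already reduces it.

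**Scale.**

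- Against the adult change of -1.01: 0.046/1.01 = 5% and 0.104/1.01 = 10%.
- Against precision: the SD of change in the middle settings is at most 0.43, so for 12 children the 95% half-width is 2.201 x 0.43/sqrt(12) = 0.27 mEq/L. The component is less than half of that.
- In-range rate: 9 of 12 (75%, close to the adult 76% in Protocol 1.2) has exact limits of 42.8% to 94.5%, above the middle no-drug rates of 11% to 22%.
- Children already in range at baseline: 12 x 0.036 = 0.4 to 12 x 0.068 = 0.8 per cohort of 12.

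**What a shift table would change.** At usual mean 5.0 in the middle setting, 20.9% of children outside the range at baseline are in range at Day 14 with no drug, against 22.2% of all children. Across the 24 settings, children with baseline above 5.0 still show 7% to 35% in range and a mean change of -0.03 to -0.29. The table separates starters from movers but not drug effect from regression to the mean.

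**The case for a change.** The strongest case for acting is that the cost is tiny and the direction of the bias does not depend on any assumed SD. The Day 14 in-range rate is a named endpoint with its own interval, and the sample-size text is framed around it. Protocol 8.6.1 tells the DSMC to weigh baseline and change for children who miss the target range, but gives no matching instruction for those who reach it. At the upper end of the 24-setting grid, 18% of children (0.18 x 12, about 2 per cohort) would start in range, and listings are a poor substitute for a cross-tabulation.

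The document facts and the direction stand. The upper end is less convincing. The largest values in that grid all need a usual mean of 4.8, below the entry threshold. In the setting behind the 37%, 28% of enrolled children would have a usual potassium at or below 5.05, which sits badly with the criterion that "the subject is expected to require treatment for hyperkalemia for at least 6 months". Means of 5.2 to 5.4 give a selected baseline of 5.50 to 5.63, near the adult 5.58 (for scale only), and a change of -0.02 to -0.12. The simulation also leaves out features that probably shrink the effect: the pseudohyperkalemia exclusion, removal of hemolyzed samples, sampling at a consistent time of day, stable medication and usual diet.

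Another possible addition is the paired change from Week 26 to the first follow-up visit. It says something about drug activity at the month-6 dose and nothing about Day 14, and treatment started after the last dose can confound it.

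**Conclusion.** No change to the plan is needed. The regression-to-the-mean component in the Day 14 change is real, but it follows from a single-arm design with an entry threshold and is not an analysis error. It is about -0.05 to -0.10 mEq/L under the middle assumptions and at most -0.27 in the wider grid; all of these sizes rest on assumed means and SDs. The choice of specimen affects only the change. The in-range rate would be the same with any baseline, and a low central baseline is laboratory disagreement.

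Every planned estimate and interval would stay as it is if the suggested tables were added, and none of them would quantify or correct the effect. The ingredients are already in the SAP: baseline distribution, change by visit, and central and local values by child. An author of the study report who wants a baseline-by-Day-14 count, or a sentence noting that uncontrolled changes include some regression to the mean, can supply either from those outputs as context, not as a correction.
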